3. A. To estimate mean all-cause and COPD-related health care resource use (HRU) and associated costs in 4 subgroups of patients who are at risk of exacerbations (i.e. a history of ≥ 2 exacerbations or ≥ 1 exacerbation leading to hospitalisation in the past 12 months) while receiving treatment with triple therapy, where the 4 subgroups are defined by the presence or absence of high blood eosinophil counts and current smoking habits
B. to compare HRU and costs with those for the total population of patients with COPD who have blood eosinophil counts available
4. To study whether the presence of high blood eosinophil counts is associated with greater all-cause and COPD-related costs in the subsequent year and to study which other easily accessible characteristics drive future costs in patients with COPD

Methods:

Study design:

An observational historical cohort study will be performed among the UK population of patients with COPD who have blood eosinophil counts available.

Patients will be characterised in a baseline year prior to the index date (ID) and outcomes will be measured in the year after ID.

Data Sources:

Analyses for sub-study 1 (association between high eosinophil counts and COPD exacerbations) will be performed in patients from OPCR. A subpopulation of patients from CPRD with linkage to Hospital Episode Statistics (HES) available will be selected for sub-studies 2–4 (association between high blood eosinophil counts and the risk of hospital re-admission for COPD and study on HRU and costs)

Study Population:

The index date (ID) will be the most recent blood eosinophil count measurement, except for sub-study 2 for which the hospital discharge date of the most recent first hospitalization for COPD within one year after a blood eosinophil count measurement will be used as ID. Eligible patients should be ≥ 40 years old and have at least 1 year of continuous data prior to and after the respective IDs, except for sub-study 2 in which patients who die or who are lost to follow-up in the outcome year are censored. Patients eligible for sub-study 1 need to be on stable treatment during the study period.

Exposures:

Only eosinophil counts measured when there was no recent (4 weeks) exacerbation recorded are considered. The primary definition of high blood eosinophil counts will be $\geq 0.45 \times 10^9/L$, based on previous work. Sensitivity analyses will be performed using ≥ 0.25 , ≥ 0.35 and $\geq 0.55 \times 10^9/L$ as the definition.

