Outcomes:

The primary outcome measure for objective 1 will be the number of COPD exacerbations during the outcome year. The number of oral steroids courses will be analysed as secondary outcome.

The occurrence of a re-admission to hospital with COPD exacerbation at any diagnostic position within 4 weeks, 12 weeks and 1 year after discharge from hospital will be the primary outcome measure for objective 2.

HRU and costs will be outcomes for objectives 3 and 4.

Sample Size Estimations:

For objective 1, a total of 1,645 patients are required for each therapy group to find a significant ($\alpha=0.05$) Rate Ratio of 1.3 as previously found with 80% power, when analysing the association between high blood eosinophil counts and the number of exacerbations, assuming 10% of patients having high blood eosinophil counts and a mean rate of events of 0.68 in patients without high blood eosinophil as found in a previous study conducted by OPRI.

For objective 2, around 10,000 patients hospitalized for COPD with a blood eosinophil count available within one year prior to ID are required for finding a hazard ratio of 1.3 for the association between a high blood eosinophil count and re-admission risk, assuming a re-admission risk of 10% within 4 weeks in patients with normal eosinophil counts.

For objective 3, a total number of 980 patients with ≥ 2 exacerbations in the baseline year while receiving triple therapy are required to find a 0.3 standard deviation greater

amount of (the logarithm) of total costs in patients with high blood eosinophil counts compared with patients with normal counts.

For objective 4, a total number of 2,200 patients are required for finding a significant difference of 0.2 standard deviations between the means of (the logarithm) of total costs of patient groups with and without high blood eosinophil counts.

Statistical Analysis:

Negative binomial regression will be performed to estimate Rate Ratios with 95% confidence intervals (CI) for the association between high blood eosinophil counts and the number of COPD exacerbations in the outcome year, stratified by different treatment options and current smoking habits, adjusted for potential confounders assessed at baseline.

Analyses will be performed in patients on different treatment regimens, adjusted for potential confounders (see paragraph 3.3.2) in two populations:

1. The full population of patients with COPD

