2.5 Study designs

2.5.1 Objective 1

The index date (ID) of objective 1 will be the most recent date of a recorded blood eosinophil count, measured at the time of stable disease, defined as no COPD exacerbation within 4 weeks prior to or at ID and no change in treatment regimen, ICS dosage and substance during the study period (Figure 1).

[figure not shown]

Figure 2. Study design objective 1

Patient's demographics and clinical characteristics will be described and potential confounders will be assessed in a baseline year prior to ID.

The association between high blood eosinophil counts (at ID) and (moderate or severe) COPD exacerbations in the subsequent year will be assessed in subgroups of patients defined by smoking status (active smoker in baseline year or not) and the following treatments in the baseline year (22):

1. Short-acting bronchodilators as required only (SABA and/or SAMA)
2. Maintenance therapy with LAMA and/or LABA
3. ICS / LABA in combination inhaler
4. Triple therapy: ICS + LABA + LAMA

The primary definition of "high eosinophil counts" will be $\geq 0.45 \times 10^9/L$, based on our previous work. Sensitivity analyses will be performed using 0.25, 0.35 and 0.55 as cut-points.

Sensitivity analyses will be performed in the subgroup of patients with COPD who have never been diagnosed with asthma, i.e., no diagnostic Read code for asthma recorded ever.

Additional analyses will be performed to evaluate whether the Medication Possession Ratio (MPR) for maintenance treatments (ICS / LAMA / LABA) modifies the associations by:

1. Including interaction terms of blood eosinophil counts and MPR into the regression model (continuous or categorical depending on best model fit) to explore whether MPR significantly modifies the association and at which values
2. Repeating analyses in patients with good adherence to ICS, using the widely used cut-point of $MPR \geq 80\%$ for therapy options 3 and 4

2.5.2 Objective 2

The ID of objective 2 will be the date of the most recent first discharge from hospital admission for COPD exacerbation occurring within one year after a blood eosinophil count measured at the time of no recent exacerbation (Figure 3). Patients will be followed after ID until re-admission or death to a maximum of one year after each index date.

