3. VARIABLES AND EPIDEMIOLOGICAL MEASUREMENTS

3.1 Determinants of COPD exacerbations

3.1.1 Definition of high blood eosinophil counts

Only eosinophil counts measured at the time of stable COPD will be eligible for selection at the most recent measurement. Stable COPD is defined as absence of a recorded COPD exacerbation within 4 weeks prior to or at the eosinophil count recording date, as our previous work showed that eosinophil counts were relevantly decreased within patients when oral corticosteroids courses were prescribed within 4 weeks prior to ID and when antibiotics were prescribed at ID.

The primary definition of high blood eosinophil counts will be $\geq 0.45 \times 10^9/L$, based on previous work. Sensitivity analyses will be performed using ≥ 0.25 , $\geq 0.35 \times 10^9/L$ and $\geq 0.55 \times 10^9/L$ as cut-points.

A sensitivity analysis adjusted for the neutrophil count / neutrophil-to-lymphocyte ratio as markers of infection (23) will be performed in patients who have these measurements available.

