3.2.2 Hospital admissions in HES linked data

1. Hospital admissions as the index date for objective 2:
Occurrence of a hospital admission (spell) for COPD exacerbation in HES linked data: ≥ 1 of the following ICD-10-CM codes in any diagnostic position (Appendix 6.1):
 - a. J44.0: Chronic obstructive pulmonary disease with acute lower respiratory infection
 - b. J44.1: Chronic obstructive pulmonary disease with (acute) exacerbation
2. Hospital re-admission as outcome event:
Occurrence of a hospital admission (spell) for COPD in HES linked data:
 - a. ICD-10 codes J44.0 or J44.1: COPD exacerbations in any diagnostic position
 - b. ICD-10 codes J40-J44: any COPD-related code as primary diagnosis

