Cox-proportional hazard regression with the time from hospital discharge date to the first re-admission date as the survival time, is performed to estimate HRs with 95% CI for the association between high blood eosinophil counts and time to re-admission over time periods

of 28 days, 12 weeks and 12 months, adjusted for potential confounders following the procedure as described for sub-study 1.

Table 1. Example of a life-table describing the time at hospital re-admission, by blood eosinophil count

Number of patients with high blood eosinophil count					Hazard probability	Survival probability
Weeks	At risk at start	Re-admission	Censored	Death		
4						
8						
12						
26						
36						
52						
Number of patients with normal blood eosinophil count					Hazard probability	Survival probability
Weeks	At risk at start	Re-admission	Censored	Death		
4						
8						
12						
26						
36						
52						
Total population					Hazard probability	Survival probability
Weeks	At risk at start	Re-admission	Censored	Death		
4						
8						
12						
26						
36						
52						

3.4.3 Outcome analyses sub-study 3

Means of the number of events per person year of follow up with standard deviations (SD) will be reported for count variables next to distributions (number and percentage) of categorical variables describing HRU in the baseline and outcome year. HRU events recorded at the index date are included in the baseline year, except medication prescriptions for which prescriptions at the index date are included in the outcome year.

Costs will be described as means with standard deviations. Costs of 4 subgroups of patients on Triple therapy at high risk of exacerbations will be compared with overall mean costs of patients with COPD in the total population by calculation of costs ratios with 95% confidence intervals, estimated by 1000 bootstrap replicates.

Non-parametric Mann-Whitney tests are performed to test differences in average costs between different populations of patients.

3.4.4 Outcome analyses sub-study 4

Two one or two-step generalized linear models with gamma distribution and log link will be used to perform regression analysis with total all-cause and total COPD-related costs as the outcome variables.

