3.6 Sample Size and Power Calculations

3.6.1 Sub-study 1

Figure 6 shows that 1,645 patients are required for each therapy group to find a significant ($\alpha=0.05$) Rate Ratio of 1.3 as previously found with 80% power, when analysing the association between high blood eosinophil counts and the number of exacerbations, assuming 10% of patients having high blood eosinophil counts and mean rate of events of 0.68 in patients without high blood eosinophil counts as previously observed.

Table 2 shows the proportions of COPD patients on different treatment options in a previous study of OPCRD patients with COPD.

Table 2. Frequencies of therapy options in a previous OPCRD study of patients with classical COPD

Therapy option	Frequency (%) in classical COPD patients
SABA and/or SAMA	18
LAMA and / or LABA	11
ICS / LABA combined	17
Triple therapy	14

Around 46,000 COPD patients from OPCRD are estimated to be available for analyses of whom one third is expected to be an active smoker. Thus, 5,000 to 8,000 OPCRD patients are estimated to be available for each treatment group of whom 3,400 to 5,500 are not active smokers.

[figure not shown]

Figure 6. Total sample size (Y-axis) required for finding different Rate Ratio's (X-axis) significant with 80% statistical power, assuming a mean rate of events of 0.68 in patients without high blood eosinophil counts and a prevalence of 10% of high blood eosinophil counts

3.6.2 Sub-study 2

A recent study performed in Scotland found hospital admission rates of 127 per 1,000 patient years for COPD exacerbations at any diagnostic position (24). In that study, 10% of re-admission occurred within 14 days.

Around 10,000 patients with a blood eosinophil count available within one year prior to a hospital admission for COPD recorded in HES are required for finding a hazard ratio of 1.3 significant ($\alpha=0.05$), assuming a baseline re-admission risk of 10% and 10% of patients having high blood eosinophils (Table 3).

Table 3. Numbers needed for finding different Hazard Ratio's

Hazard Ratio high vs normal	Re-admission risk in patients with normal eosinophil counts	Prevalence of high eosinophil count	Total number of COPD patients required	Numbers needed normal / high	Power at $\alpha=0.05$
1.4	10%	10%	5,729	5,161 / 568	80%
1.3	10%	10%	10,079	9,080 / 999	80%
1.2	10%	10%	22,442	20,218 / 2224	80%

3.6.3 Sub-study 3

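### Sub-study 2's index rule lets a re-admission replace the admission it followed, so the 1-year re-admission risk is understated; 'first' is also undefined

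*Protocol*

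**What the plan says.** Section 2.5.2 sets the index date for objective 2 as "the date of the most recent first discharge from hospital admission for COPD exacerbation occurring within one year after a blood eosinophil count". The synopsis (Study Population) has a near-identical rule: "the hospital discharge date of the most recent first hospitalization for COPD within one year after a blood eosinophil count measurement". Neither explains 'first', and neither requires a period free of admissions before the index.

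On follow-up, Section 2.5.2 says: "Patients will be followed after ID until re-admission or death to a maximum of one year after each index date". The synopsis (Outcomes) states that re-admission "within 4 weeks, 12 weeks and 1 year after discharge from hospital will be the primary outcome measure for objective 2". Section 3.4.2 fits Cox models over periods "of 28 days, 12 weeks and 12 months, adjusted for potential confounders following the procedure as described for sub-study 1".

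Two further rules matter:

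- Section 3.1.1 makes a count eligible only in stable disease: "Stable COPD is defined as absence of a recorded COPD exacerbation within 4 weeks prior to or at the eosinophil count recording date".
- Section 3.2.2 defines the index admission by J44.0 or J44.1 in any position, and part (a) of the re-admission outcome uses the same set: "ICD-10 codes J44.0 or J44.1: COPD exacerbations in any diagnostic position". Part (b) adds any J40-J44 code as primary diagnosis.

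**The concern.** Because index and outcome share a code set, a re-admission can itself qualify as an index admission. Because the latest qualifying admission is chosen, it will be the index whenever it qualifies. An admission keeps its place only if no later admission of the same patient qualifies, so selection depends on what happened after it, including the outcome.

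The patients who lose an event are those who were re-admitted after a fresh stable count. Their follow-up restarts at the later admission. At stake is the 1-year re-admission risk, which has its own life-table rows, Kaplan-Meier curve and Cox model. Adjusting for the baseline confounders in Section 3.3.2 does not repair a selection made on later events.

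**Working it through.** **Step 1. The plan's own figure.** Inputs from Section 3.6.2 and Table 3: hazard ratio 1.3, "assuming a baseline re-admission risk of 10% and 10% of patients having high blood eosinophils", two-sided alpha 0.05, 80% power, groups 9,080 / 999 (k = 999/9,080 = 0.11). The synopsis places the 10% risk at 4 weeks. The Freedman log-rank formula gives:

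- Events: E = (1.960 + 0.842)² × (1 + k·HR)² / [k(1 − HR)²] = 7.849 × 1.143² / (0.11 × 0.09) = 1,036.
- Risk in the high group: 1 − 0.9^1.3 = 0.128.
- Patients: N = E(1 + k) / (0.10 + 0.11 × 0.128) = 10,079.

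Table 3 says 10,079. The rows for 1.4 (5,729) and 1.2 (22,442) also match exactly.

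**Step 2. The mechanism, with illustrative dates.** Stable count on day 0, discharge A1 on day 100, new stable count on day 200, re-admission A2 on day 300. A2 is the first admission after the day-200 count, lies within a year of it, and is later than A1. So A2 is the index, and the A1-to-A2 event at 200 days is not counted. If instead A2 fell on day 120, no eligible count could lie between the two, because the 4-week rule blocks counts until day 128. A1 would stay the index and the event would be kept.

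The time available for an intervening count is therefore none for an event within 4 weeks, at most 84 − 28 = 56 days for one within 12 weeks, and at most 365 − 28 = 337 days for one within a year.

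**Step 3. Size, by simulation.** There is no closed formula, and counts per patient per year are not given, so they are assumed. Set-up:

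- 20,000 patients per scenario and an 8-year window.
- Admission rate before the first admission: 0.127 per year (Section 3.6.2) times a gamma frailty with mean 1 and variance 1.
- Hazard after discharge set to give 10% at 4 weeks: −ln(0.9)/(28/365) = 1.373 per year. It is 0.6 of that in weeks 4-12 and 0.35 of it to one year, then returns to the earlier rate.
- Counts at random times, ineligible within 4 weeks after an admission.

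The 1-year risk built in is 1 − exp[−(0.105 + 0.6 × 1.373 × 56/365 + 0.35 × 1.373 × 281/365)] = 1 − exp(−0.602) = 45%.

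| Counts per year | 12-week risk, earliest v most recent | 1-year risk, earliest v most recent | 1-year events turned into an index |
|---|---|---|---|
| 0.25 | 19.8% v 19.4% | 46.1% v 43.3% | 8% |
| 0.5 | 20.7% v 20.8% | 45.6% v 41.7% | 13% |
| 1 | 20.0% v 20.5% | 45.0% v 36.5% | 24% |
| 2 | 21.3% v 19.9% | 46.4% v 31.3% | 35% |

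No 4-week event is lost in any row. At 12 weeks, 1% to 6% of events are lost. The earliest rule recovers the built-in 45% within sampling error; the most recent rule falls short by about 2 points at the lowest testing rate and 45 − 31 = 14 at the highest.

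Other hazard assumptions agree in direction:

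- 0.2 admissions per year, with the hazard tripled for about 90 days after discharge: 35% v 32%, 33% v 27% and 32% v 23% at 0.5, 1 and 2 counts per year. The 12-week risk is lower by about 0 to 2 points.
- 0.2 per year, with gamma frailty and a raised post-discharge hazard: 42% v 38%, 39% v 33% and 38% v 27%. With an extra count after 30% of admissions: 40% v 28%. The 12-week loss is about 0.5 to 3 points.

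**Step 4. The hazard ratio.** This used a true within-patient ratio of 1.3, which frailty attenuates under either rule. Ratios are earliest v most recent.

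| Re-testing | Ratio |
|---|---|
| Equal; 0.5, 1, 2 counts per year | 1.20 v 1.19; 1.20 v 1.22; 1.23 v 1.21 |
| Extra count after 30% of admissions, both groups | 1.22 v 1.26 |
| Extra count, 30% normal v 35% high | 1.23 v 1.19 |
| Extra count, 30% normal v 50% high | 1.24 v 1.04 |
| Extra count, 30% normal v 20% high (separate run) | 1.22 v 1.32 |

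**The case against.** Objective 2 asks a comparative question, and with equal re-testing the ratio barely moves. The study is powered on a 4-week risk that the rule leaves alone. Both points stand and limit the severity.

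The 1-year loss rests on a testing frequency that the documents do not give; eligibility needs only one count. If counts are rare the loss is small: at 0.25 to 0.5 per year, 8% to 13% of events. This also stands. Section 3.5.2 calls full blood counts part of the routine work-up in COPD, which makes repeat counts plausible but does not give a rate.

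The simulations treat every re-admission as able to become an index. Re-admissions that count only under part (b), through other J40-J44 codes as primary diagnosis, cannot. Exacerbations treated outside hospital would also make some counts ineligible. Both would shrink the loss for a given testing rate.

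'First' might mean first ever, or first after an admission-free period. The former would leave 'most recent' with nothing to choose between. The latter could prevent the problem if the period were long enough, but none is stated, and the design figure is not available to settle it.

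Three stronger inferences are tempting, and the documents do not support them:

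- That many 12-week events vanish. The 4-week stability rule leaves too little time for an intervening count.
- That the hazard ratio is driven to 1. This needs a large difference in re-testing by eosinophil group, and none is documented.
- That the index is simply the latest eligible discharge. That reading would remove most events (4-week risk about 0.2-0.6%, 1-year about 6-20%), but it gives 'first' no role. It is a reason to define the word, not a description of the plan.

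**Conclusion.** The point holds in a limited form. On the natural reading, the index is chosen with knowledge of later admissions, and the 1-year re-admission risk is understated. The size is roughly 3 to 14 percentage points for 0.5 to 2 randomly timed counts per year, and about 2 points at 0.25 per year. Routine testing after most discharges would push it higher: one run with an extra count after 60% of admissions gave 35% v 15%. All these figures rest on assumed hazards and testing rates. They show a range, not an estimate for this database.

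The 4-week risk and the sample size of 10,079 are unaffected, and the 12-week loss is about 0 to 3 points. Bias in the hazard ratio is hypothetical: it could go in either direction, and only if re-testing differs by eosinophil group. This should be fixed, because the affected quantity is a named primary outcome and the remedy is cheap, but it does not undermine the sub-study as a whole.

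**What to change.** In Section 2.5.2 and, in matching words, in the synopsis:

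- State that 'first' means the first J44.0/J44.1 admission after the qualifying count, and state whether an admission-free period is required.
- Define the index as the earliest discharge in the study window that meets criteria 7a and 7b (Section 2.3), chosen without reference to later admissions.
- Use the last eligible count before that admission as the exposure.
- Add calendar year of the index admission to the covariates.
- Keep the most recent rule as a sensitivity analysis.

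The cost is a short text change. The data are the same, and so are the patients, since anyone with a most recent qualifying admission also has an earliest one. The downside is that index admissions are older on average, which the calendar-year term addresses.

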3. VARIABLES AND EPIDEMIOLOGICAL MEASUREMENTS

3.1 Determinants of COPD exacerbations

3.1.1 Definition of high blood eosinophil counts

Only eosinophil counts measured at the time of stable COPD will be eligible for selection at the most recent measurement. Stable COPD is defined as absence of a recorded COPD exacerbation within 4 weeks prior to or at the eosinophil count recording date, as our previous work showed that eosinophil counts were relevantly decreased within patients when oral corticosteroids courses were prescribed within 4 weeks prior to ID and when antibiotics were prescribed at ID.

The primary definition of high blood eosinophil counts will be $\geq 0.45 \times 10^9/L$, based on previous work. Sensitivity analyses will be performed using ≥ 0.25 , $\geq 0.35 \times 10^9/L$ and $\geq 0.55 \times 10^9/L$ as cut-points.

A sensitivity analysis adjusted for the neutrophil count / neutrophil-to-lymphocyte ratio as markers of infection (23) will be performed in patients who have these measurements available.

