3.2 Outcomes

3.2.1 COPD exacerbations

The primary outcome for sub-study 1 will be the number of COPD exacerbations in the outcome period, defined as the occurrence of one or more of the following events:

- a. Respiratory-related hospital attendance / admission AND/OR
- b. Respiratory-related A&E attendance AND/OR
- c. An acute oral corticosteroid course AND/OR
- d. Antibiotics prescribed with evidence of a lower respiratory consultation

Where ≥ 1 of these events occur within 2 weeks of each other, they will be considered to be the result of the same exacerbation (and will only be counted once).

The number of acute oral corticosteroids courses will be analysed as secondary outcome for sub-study 1.

A sensitivity analysis will be performed with a more specific (but less sensitive definition) of acute oral corticosteroids courses with evidence of a lower respiratory consultation (Read code for lower respiratory consultation with prescription).

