3.5.2 Limitations

1. The datasets represent information collected for clinical and routine use rather than specifically for research purposes. Although extensive quality control and validity checks are conducted on the practice level, the validity and completeness of individual patient records cannot be assessed.
2. Exposure to drugs is estimated based on the number of prescribed doses over time periods, which does not guarantee correct use of all doses included.
3. OPCRD doesn't provide detailed information on GP consultations. The number of GP consultations may therefore be overestimated.
4. Although full blood count measurements are part of the routine work up in Primary Care for patients with COPD, patients with blood eosinophil counts available may not be representative of the total population of COPD patients.

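### The stable-count rule leaves in eosinophil counts taken on a day with an antibiotic prescription that had no lower respiratory consultation, although the rule's own rationale does not exempt them

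*Protocol*

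**What the plan says.** Section 3.1.1 states the rule: "Stable COPD is defined as absence of a recorded COPD exacerbation within 4 weeks prior to or at the eosinophil count recording date". Section 2.3 item 3 makes it an inclusion criterion for every objective, and section 2.5.1 repeats it for objective 1.

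Section 3.1.1 gives two findings from the team's previous work as the reason: counts were lower when oral steroid courses had been "prescribed within 4 weeks prior to ID and when antibiotics were prescribed at ID". The second finding, on antibiotics, carries no restriction to respiratory prescribing.

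The protocol's only general definition of an exacerbation is in section 3.2.1, where any one of four components is enough. Item c is "An acute oral corticosteroid course AND/OR", with no consultation required. Item d is "Antibiotics prescribed with evidence of a lower respiratory consultation". Events within 2 weeks of each other are treated as one exacerbation, and the section does not say which date the combined episode takes. Section 2.4 excludes chronic oral corticosteroid treatment.

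Section 3.1.1 also plans a sensitivity analysis adjusted for neutrophil count or neutrophil-to-lymphocyte ratio, in patients who have those measurements.

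**The concern.** The rule exists to keep temporarily lowered counts out of the exposure. It does so through the exacerbation definition, and for antibiotics that definition is narrower than the evidence cited for the rule. A patient whose usual count is above the cut-point, but whose latest count was taken on the day of an antibiotic prescription without a lower respiratory consultation, can enter the reference group.

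If such patients also go on to have more exacerbations, the reference rate rises and the rate ratio falls. The same count definition supplies the exposure for all four objectives, so the gap is not confined to sub-study 1.

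**Working it through.** **Step 1: rationale against rule.**

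| Situation at the count | Cited in 3.1.1 as lowering counts? | Removed by the rule read with 3.2.1? |
|---|---|---|
| Acute oral steroid course in the prior 4 weeks | Yes | Yes, item c; one case depends on episode dating (step 2) |
| Chronic oral steroids | Not addressed | Yes, excluded by 2.4 |
| Antibiotic on the date, with lower respiratory consultation | Yes | Yes, item d |
| Antibiotic on the date, without it | Yes, no exemption stated | No |

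The last row is the gap.

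**Step 2: the merging case for steroids.** Take a first event 29 days before the count and a steroid course 15 days before it. The gap is 29 − 15 = 14 days, so they form one episode. If that episode is dated at its first event, it lies outside 28 days and the count passes, although a course fell inside the window. Under that dating, a course 15 to 28 days before the count can be missed. If each event date is checked, none is missed. The protocol does not say which applies.

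**Step 3: scale.** No figure in the plan measures the gap, so this is an illustration. From section 3.6.1: 10% high counts and a rate ratio of 1.30. Assumed: a share f of counts is affected, the proportion recorded as high among them is h instead of 0.10, and their later exacerbation rate is k times that of others. With the unaffected normal rate set to 1:

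- Recorded high: H = [(1−f)(0.10)(1.3) + f·h·1.3k] / [(1−f)(0.10) + f·h]
- Recorded normal: N = [(1−f)(0.90) + f{0.90k + (0.10−h)·1.3k}] / [(1−f)(0.90) + f(1−h)]
- Observed RR = H / N

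For f = 0.05, h = 0.05, k = 1.5: H = 0.128375 / 0.0975 = 1.3167; N = 0.927375 / 0.9025 = 1.0276; RR = 1.281.

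For h = 0.07 instead: H = 0.130325 / 0.0985 = 1.3231; N = 0.925425 / 0.9015 = 1.0265; RR = 1.289.

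| f | k = 1.0 | k = 1.5 | k = 2.0 |
|---|---|---|---|
| 0.02 | 1.300 | 1.292–1.295 | 1.285–1.291 |
| 0.05 | 1.299 | 1.281–1.289 | 1.265–1.279 |
| 0.08 | 1.298–1.299 | 1.271–1.283 | 1.246–1.268 |

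(The ranges run from h = 0.05 to h = 0.07.) Nearly all the attenuation comes from k. With k = 1 the ratio barely moves.

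**Step 4: power.** The plan's 1,645 per therapy group is approximated by a square-root Poisson comparison (two-sided α 0.05, 80% power, rates 0.68 and 0.68 × 1.3 = 0.884):

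n = (1.960 + 0.842)² × 0.25 × (1/0.1 + 1/0.9) / (√0.884 − √0.68)² = 7.849 × 2.778 / 0.01336 ≈ 1,632.

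Suppose a share m of truly high counts is recorded as normal, unrelated to outcome. Recorded prevalence is then q = 0.1(1−m), and the reference rate is (0.9 × 0.68 + 0.1m × 0.884)/(1−q). For m = 5% the reference rate is 0.61642/0.905 = 0.6811, the RR is 1.298 and n is 1,729. For m = 20% the RR is 1.292 and n is 2,092. Section 3.6.1 expects 5,000 to 8,000 patients per treatment group, 3,400 to 5,500 of them not active smokers.

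**The case against.** The strongest reply is that section 3.2.1 builds exacerbations from the very prescriptions named in 3.1.1. For steroids this stands. A reader might infer that the rule ignores recent steroid courses altogether, but item c counts any acute course by itself and 2.4 removes chronic users. Only the undated merged episode remains. The merging sentence is a counting rule for the outcome, and how episodes are dated is a detail a protocol can leave to the SAP. That part is a request for clarification, not a demonstrated error.

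A second reply is that 3.1.1 summarises unseen work and does not say the fall occurred with non-respiratory antibiotics. That is fair, and it is why the effect cannot be sized. But the sentence does not restrict itself to respiratory prescribing either, and the rule does.

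A third is that the neutrophil analysis already deals with infection at the count. It does so in part. It is a sensitivity analysis in a subset, and it adjusts for infection markers without removing the lowered count or returning the patient to the high group. The alternative cut-points use the same eligible counts.

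A reader might also take the limitation that "OPCRD doesn't provide detailed information on GP consultations" as proof that respiratory consultations are often unrecorded. Section 3.5.2 draws a different consequence from it, namely overestimated consultation numbers. It also concerns the sub-study 1 database only. It gives little support here.

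**Conclusion.** The point holds for antibiotics. A count taken on a day with an antibiotic prescription that lacks evidence of a lower respiratory consultation is eligible, and the protocol's own reason for the rule does not exempt it. For steroids nothing more is established than an unstated episode date.

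The expected effect is a small bias towards the null: about 1.28 to 1.29 for a true 1.30 in the middle case, and 1.246 to 1.295 across the grid with k of 1.5 or 2.0. All of this rests on assumed shares, on counts being lowered on such days, and on these patients exacerbating more often later. The documents supply none of these figures. The low end needs the worst value of all three inputs at once. If misrecording is unrelated to outcome, the shift is at most to 1.292, even with 20% of high counts misrecorded. Someone might infer that power or the main conclusion is at risk; the patient numbers expected in section 3.6.1 do not support that. This is a minor but worthwhile tightening of the exposure definition.

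**What to change.** In sections 3.1.1, 2.3 item 3 and 2.5.1:

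- Add to the eligibility rule that no antibiotic was prescribed on the count date. At minimum, plan a sensitivity analysis that excludes such counts.
- Refer to section 3.2.1 for the exacerbation components. That section introduces its definition only as the sub-study 1 outcome, while the count rule serves all four objectives.
- State that the 4-week check applies to the date of each component event, not to the start of a merged episode.
- If the latest count fails, use the next most recent eligible one.

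The cost is a few lines of wording and one filter on prescription data already needed to build the exacerbation variable. A few patients will get an earlier index date or drop out.
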